12 OCT 2020

- Pooled analysis of InterMune-sponsored CAPACITY 2 and CAPACITY 1 (2403 mg/d vs. placebo) – At 72 weeks, categorical change in FVC  $\geq$  10%, progression-free survival and mean change in 6MWT were significant ( $p = 0.003, 0.025$  and  $0.0009$ , respectively).
- Meta-analysis of InterMune CAPACITY 2, CAPACITY 1, and Shionogi SP3 (high dose only) – Demonstrated a reduced disease progression with a hazard ratio of 0.70; 95% CI 0.56-0.88;  $p = 0.002$  and clearly excluded no-effect from serial lung capacity treatment measurements.
- Adverse events (AEs) of InterMune CAPACITY 2 and CAPACITY 1 – The most commonly reported ( $\geq 10\%$ ) and important AEs during clinical study experience at a dose of 2403 mg/d compared to placebo, respectively, were nausea (32.8% vs. 13.3%), rash (28.7% vs. 8.6%), fatigue (22.3% vs. 13.3%), diarrhea (21.7% vs. 13.5%), dyspepsia (16.8% vs. 5.5%), photosensitivity reaction (12.2% vs. 1.7%) and elevated liver enzymes ( $>3X$  upper limit of normal aspartate aminotransferase/alanine aminotransferase (AST/ALT): 4.1% vs. 0.6%). Serious adverse events (SAEs) were recorded at similar frequencies between active and placebo groups. In the InterMune open-label Phase 3 extension AE and SAE observations out to 3 years treatment were similar in event and frequency.
- InterMune-sponsored ASCEND (2403 mg/d vs. placebo) – At 52 weeks, categorical change in FVC  $\geq$  10%, progression-free survival and categorical change in 6MWT were significant ( $p = 0.000001, 0.0001$  and  $0.036$ , respectively).

The recommended daily dose of Esbriet® for patients with IPF is three 267 mg capsules three times a day with food for a total of 2403 mg/d. Doses above 2403 mg/d are not recommended for any patient. Upon initiating treatment, it is recommended that the dose be titrated over a 14-day period.

During the InterMune CAPACITY studies, 48% of patients were dose-reduced or intermittently stopped due to AEs. Dose reductions were permitted to 50% before discontinuation. 6.2% more patients in the 2403 mg/d pirfenidone group discontinued treatment due to an AE than those on placebo (14.8% vs. 8.6%, respectively).

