## **8.7. Missed Doses and Dose Modifications**

Doses that are missed can be taken in a 24-hour period, as long as doses are 4 hours apart.

In the event of excessive coughing while drug administration at home, the patient will contact the site to determine how to proceed. Salbutamol may be prescribed to be administered prior to dosing, as described in section 8.6, if deemed necessary by the investigator.

If AP01 is stopped during treatment due to intolerance, restart dosing when the patient has improved. The initial dose after restarting should be observed for tolerance.

It is recommended to reduce the 100 mg twice daily dose to 50 mg twice daily if the patient cannot tolerate the 100 mg dose. If the 50 mg twice daily dose cannot be tolerated, the patient may have their dose reduced to 50 mg once daily.

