3.5. Determination of Sample Size

This is an open-label study to determine safety and tolerability of AP01 50 mg once daily or 100 mg twice daily; both regimens being administered using the eFlow. With 50 patients per group, we have a 92% chance of detecting an AE with a true population rate of 5%, as displayed in Table 1:

Table 1: Probability of observing adverse events

	Actual probability of event		
	1%	5%	10%
Chance of observing ≥ 1 event	0.395	0.923	0.995

The Phase 3 study of oral pirfenidone in patients with IPF (ASCEND)¹ showed a standard deviation (SD) of 4.5 based on the imputed mean change in % of predicted FVC at Week 26. Assuming a SD of 4.5, with 50 patients per group, a two-sided 95% confidence interval (CI) for mean change from baseline in % of predicted FVC will extend 1.25 from the observed mean. The ASCEND¹ study showed a decrease of 1.5 and 3.9 in % of predicted FVC at Week 26 in the pirfenidone and placebo groups, respectively. Table

This document is confidential.

SAP Version: 3.0 (15JUL2021)
Controlled Document ID: **3903A.01**, Effective Date 29-Oct-2018
Filing requirements: TMF

Page 14 of 52

Statistical Analysis Plan

Sponsor: Avalyn Pharma, Inc.; Protocol No.: AP01-002

2 shows results of the ASCEND¹ active and placebo groups and potential observed differences in the AP01-002 study, assuming a similar SD.

Because we have no prior data on efficacy outcomes with our compound, we are unable to make well-informed predictions of effect size or variability. In lieu of that information, we have included some estimates of confidence intervals based on prior oral pirfenidone studies; however, we cannot be confident that our product will behave similarly and would not base hypothesis tests on this information. This study will give us an idea of which endpoints are most likely to be positively impacted by our product as well as solid estimates of both effect size and variability. In addition, if the effect is due to AUC or multiple peaks/day in the Epithelial Lining Fluid (ELF) rather than peak levels, based on our modeling from the BAL cohort in the AP01-001 study, we have around 75% power to show a difference between groups. With this sample size, we can be confident on selecting dosing regimen(s) for future trials.

Table 2: Observed and potential change in FVC

	ASCEND¹ Placebo (n = 262)	ASCEND¹ Active (n = 255)	AP01-002 Potential Scenarios (n = 50)		

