4.4. Safety Endpoints

- Treatment-emergent adverse events (AEs)
- Change from pre-dose to post-dose FEV₁ after initial dose
- Treatment-emergent deaths
- Treatment-emergent changes in clinical laboratory findings
- Changes in Vital signs.

Statistical Analysis PlanSponsor: Avalyn Pharma, Inc.; Protocol No.: AP01-002

5. Analysis Sets**5.1. Safety Set**

The Safety Set (SAF) will include all randomized patients who were administered at least one dose of study medication. Patients will be analyzed according to treatment received. The SAF will be used for all analyses of safety endpoints.

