All relevant patient data will be included in listings. All patients entered into the database will be included in patient data listings.

Pulmonary function tests (PFTs) (including D_{LCO}) are performed at each study visit.

The following PFTs will be performed at all visits (including Screening) using spirometry (and documented on the PFT eCRF form):

- FVC Liters (L)
- FEV₁ Liters (L)
- % Predicated FVC
- % Predicted FEV₁.

Pre-dose and post-dose spirometry will be performed at the Baseline visit.

At every visit, D_{LCO} ($\text{mL}/\text{min}^{-1}/\text{mmHg}^{-1}$) and % Predicted D_{LCO} will be obtained using the site's standard methodology.

FEV₁/FVC ratio will be derived as: $100 \times \text{FEV}_1/\text{FVC}$.

For comparisons to baseline, data from Visit 2 prior to the first dose of study drug will be used as baseline, unless otherwise noted. For PFTs, the pre-dose result will be used as baseline. Subgroup analyses will be performed based on baseline groupings for FVC, region, age, sex, D_{LCO} and progression-related biomarkers (CXCL13, CCL18, MMP3).

If either regimen is eliminated based on Part A outcomes, patients may be switched to the selected regimen for the remainder of their participation. Data summaries will be created to mimic this switch by using the following treatment grouping for Part B: (1) randomized to 100 mg twice daily; (2) randomized to 50 mg once daily and stayed on 50 mg once daily; (3) randomized to 50 mg once daily and switched to 100 mg twice daily; (4) randomized to 50 mg once daily total [groups 2 and 3 combined]; (5) overall total for Part B data. Descriptive within-patient analyses will be included for those patients who switch from 50 mg once daily to 100 mg twice daily. These analyses will include spider plots of change from baseline showing when the dose switch took place. Data listings will include a variable to denote the regimen switch and flag the time of the switch for affected patients.

No formal hypothesis tests are planned.

This document is confidential.

SAP Version: 3.0 (15JUL2021)
Controlled Document ID: **3903A.01**, Effective Date 29-Oct-2018
Filing requirements: TMF

Page 22 of 52

Statistical Analysis PlanSponsor: Avalyn Pharma, Inc.; Protocol No.: AP01-002

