- For each patient, the percent compliance with the patient's care plan will be derived cumulatively across all visits across all patient doses as 100 times (the total number of used ampoules returned divided by the total number of ampoules that would be used if they were fully dosing for the number of days between visits minus the number of ampoules that would be missed if following instructions to reduce or interrupt dose). If a subject discontinues early, the denominator will be the total number of ampoules, which would be used up to, and including the date of discontinuation. Percent compliance will be summarized by treatment group with descriptive statistics. The percent compliance will be categorized ($\geq 80\%$, 60- $<80\%$, 40- $<60\%$, 20- $<40\%$ and $<20\%$) and summarized by treatment group with frequency counts and percentages. The percent compliance will be calculated overall and separately for each dosing regimen for those patients who switch over from 50 mg once daily to 100 mg twice daily in Part B.
- The number of patients who had any days where all doses were missed will be summarized cumulatively across all visits by treatment group with frequency counts and percentages. For those patients who had any days where all doses were missing, the maximum number of days between doses will be summarized cumulatively across all visits by treatment group with descriptive statistics.

This document is confidential.

SAP Version: 3.0 (15JUL2021)
Controlled Document ID: **3903A.01**, Effective Date 29-Oct-2018
Filing requirements: TMF

Page 28 of 52

Statistical Analysis PlanSponsor: Avalyn Pharma, Inc.; Protocol No.: AP01-002

All recorded information for study medication administration and accountability for AP01 will be listed.

All recorded information for Nebulizer Training, Nebulizer and Nebulizer handset accountability will be listed.

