10.1. Adverse Events / Adverse Drug Reactions

An adverse event (AE) is any untoward medical condition that occurs in a patient while participating in this clinical study. Adverse events will be coded according to the Medical Dictionary for Regulatory Activities (MedDRA 21.1 or higher) terminology and the severity of the toxicities will be graded according to the National Cancer Institute (NCI) Common Terminology Criteria for Adverse Events (CTCAE), v5.0, where applicable. An adverse drug reaction (ADR) means any AE caused by a drug or biologic.

Treatment-Emergent Adverse Events (TEAEs) are those adverse events/adverse drug reactions that are recorded during or following the initiation of AP01 medication administration, and do not necessarily have a causal relationship to the use of the study medication. Treatment-Emergent Adverse Events (simply referred to as adverse events in summary tables) will be summarized.

The following adverse event summary tables will be summarized by treatment group and combined over both treatment groups:

- 1) An overall summary with the number and percentage of patients reporting AEs, serious AEs, grade 3 or higher AEs, treatment-related AEs, AEs leading to study treatment (AP01) discontinuation and AEs with outcome of deaths. In addition, this overall summary will be performed for each subgroup listed in Section 6.6.
- 2) AEs overall and by system organ class and preferred term. In this summary, a patient is counted once at the system organ class and once at each preferred term within the system organ class. In addition, this summary will be performed for each subgroup listed in Section 6.6.
- 3) A separate summary of respiratory [SOC respiratory, thoracic and mediastinal disorders] TEAEs by Preferred Term and summary of tolerability including cough due to drug administration and bronchospasm after in-clinic drug administration) will be performed by each subgroup listed in Section 6.6.

This document is confidential.

Statistical Analysis PlanSponsor: Avalyn Pharma, Inc.; Protocol No.: AP01-002

- 4) AEs overall and by system organ class, preferred term and highest CTCAE grade.

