In this summary, a patient is counted once at the highest grade for which the event occurred in the system organ class and the highest grade for each unique preferred term within that system organ class. Therefore, patients may only contribute once to each preferred term and once to each system organ class. The missing severity grade will be reported in a separate category.

- 5) Study-treatment-related AEs overall and by system organ class and preferred term.

All those AEs with relationship to AP01 marked as “Possibly Related” or “Probably Related” or missing will be reported in the table.

- 6) Study-treatment related AEs by system organ class, preferred term and Highest CTCAE grade
- 7) AEs leading to study treatment termination by system organ class and preferred term
- 8) AEs leading to study treatment termination by system organ class, preferred term and highest CTCAE grade
- 9) CTCAE Grade 3 or higher AEs, overall and by system organ class and preferred term

A Serious Adverse Event (SAE) is an AE that falls into one or more of the following categories:

- a. Results in death
- b. Is life-threatening
- c. Requires inpatient hospitalization or prolongation of existing hospitalization
- d. Results in persistent or significant disability or incapacity
- e. Is a congenital anomaly/birth defect
- f. Is any other important medical event

Serious adverse events will be summarized by treatment group and combined over both treatment groups.

- 1) SAEs overall and by system organ class and preferred term.

In this summary, a patient is counted once at the system organ class and once at each preferred term within the system organ class.

- 2) SAEs overall and by system organ class, preferred term and highest CTCAE grade.

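### In Part A the discontinuation rows are not like for like between regimens, because no by-arm table counts dose reductions or attributes at-home interruptions to intolerance

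*SAP*

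**What the plan says.** **Dose steps.** Protocol 8.7 states: "It is recommended to reduce the 100 mg twice daily dose to 50 mg twice daily if the patient cannot tolerate the 100 mg dose". Its next sentence allows a further reduction to 50 mg once daily, which is the other arm's regimen. No step is written for a patient assigned 50 mg once daily. Stopping for intolerance and later restarting is open to both arms.

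**Adverse-event tables.** In SAP 10.1 the overall summary covers "treatment-related AEs, AEs leading to study treatment (AP01) discontinuation and AEs with outcome of deaths". The detailed tables add "AEs leading to study treatment termination by system organ class and preferred term", and the same again by highest grade. No other action on study drug has a table.

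**Exposure tables.** SAP 7.5 plans total dose, percent compliance against the full regimen, and the number of patients with days when every dose was missed. It also plans care-plan compliance, whose denominator is the full-dosing ampoule count "minus the number of ampoules that would be missed if following instructions to reduce or interrupt dose". SAP 6.1, 6.2.8 and 7.1 track the Part B switch from 50 mg to 100 mg in detail. Patients randomized to 100 mg twice daily stay one undivided group.

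**Column assignment.** For the Safety Set, SAP 5.1 says: "Patients will be analyzed according to treatment received". Protocol 11.2 says patients are analyzed as randomized. SAP section 12 lists only the added Full Analysis Set as a change from the protocol.

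**Purpose.** Safety and tolerability is the primary objective (SAP 3.1), and comparing the two regimens to guide later dosing is a secondary one (SAP 3.2). On testing, SAP 6.1 says: "No formal hypothesis tests are planned".

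**The concern.** A patient who cannot tolerate the assigned regimen can be reduced, interrupted or stopped. In Part A the first outcome is written for one arm only, and the planned tables by action taken count only the last. Two arms with the same underlying intolerance can therefore show different discontinuation counts, and arms that differ can show the same count. The direction is predictable: any patient whom a reduction keeps on 100 mg-arm treatment leaves the discontinuation row, and no other row picks that patient up.

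At stake is how many patients could sustain 100 mg twice daily as assigned. A tolerability study meant to guide future regimens should answer that directly, and a reader of the planned tables could not extract it.

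**Working it through.** **1. The plan's own safety figure.** With n = 50 per arm, the chance of at least one event is 1 − (1 − p)^50. This gives 0.395 at p = 1%, 0.923 at 5% and 0.995 at 10%. Table 10 of the protocol and Table 1 of the SAP reproduce, and no stated number is in dispute.

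**2. Outcomes set against tables (Part A).**

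| Outcome of intolerance | 100 mg twice daily | 50 mg once daily | Table by arm |
|---|---|---|---|
| Dose reduced | two steps written | none written | none |
| Interrupted at home, restarted | possible | possible | days with all doses missed and longest gap, no cause given |
| Stopped | possible | possible | adverse events leading to discontinuation |

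**3. Effect on the discontinuation row.** Let q be the rate of intolerance that would end treatment if no lower dose were available, and f the share of such 100 mg patients whom a reduction keeps on drug. The documents give neither, so both are assumed. The tabulated 100 mg rate is q × (1 − f); the tabulated 50 mg rate is q.

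| f | Truth 20% in both arms: expected count of 50 (100 mg vs 50 mg) | Truth 20% vs 10%: tabulated rates | Tabulated difference |
|---|---|---|---|
| 0 | 10 vs 10 | 20% vs 10% | +10 points |
| 25% | 7.5 vs 10 | 15% vs 10% | +5 points |
| 50% | 5 vs 10 | 10% vs 10% | 0 |
| 75% | 2.5 vs 10 | 5% vs 10% | −5 points |

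In the first scenario, counting reduced or discontinued patients together gives 10 vs 10 at every f.

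**4. Chance of seeing anything in that row.** At q = 5%, the chance of at least one tabulated discontinuation in the 100 mg arm is 1 − (1 − 0.05 × (1 − f))^50. It is 0.923 at f = 0, then 0.852, 0.718 and 0.467 at f = 25%, 50% and 75%.

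**5. Whether the compliance tables fill the gap.** By protocol 8.3.5, 100 mg twice daily uses 4 ampoules a day. At 50 mg each, 50 mg twice daily uses 2 and 50 mg once daily uses 1. Full dosing over 28 days is 28 × 4 = 112.

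- Reduced to 50 mg twice daily for the last 14 days: used 14 × 4 + 14 × 2 = 84. Plain compliance is 84/112 = 75%; care-plan compliance is 84/(112 − 28) = 100%.
- Reduced to 50 mg once daily for the last 14 days: used 56 + 14 = 70. Plain 70/112 = 62.5%; care-plan 70/(112 − 42) = 100%.
- Instructed to interrupt for 7 days with no reduction: used 21 × 4 = 84. Plain 75%; care-plan 84/(112 − 28) = 100%.
- Missed the same 28 ampoules without instruction: plain 75%; care-plan 84/112 = 75%.

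The two measures together separate instructed from uninstructed shortfall. They do not separate a reduction from an interruption (first and third cases are identical), do not count reduced patients, and do not give a reason. The table of days with all doses missed does not pick up a reduced patient who still doses daily.

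There is also a question whether these measures can be computed as written. SAP 7.5 counts used ampoules returned, while protocol 8.8.1 has patients dispose of used ampoules and bring back unused ones.

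**The case against.** The strongest reply is that much about tolerability is tabulated by arm already. SAP 6.6 and 10.1 summarize cough due to drug administration and bronchospasm. SAP 7.5 and 10.6 cover second observed doses, salbutamol use, interrupted inhalations and FEV1 drops of 15% or more. An adverse event that prompts a reduction still counts by arm, term, grade and relatedness. This stands, and it defeats a reading that intolerance appears only as discontinuation. It also defeats a reading that the primary safety analysis under-counts: the protocol synopsis builds that analysis on treatment-emergent event rates, post-first-dose spirometry, deaths, laboratory findings and vital signs, and discontinuation is not its measure. The gap that remains is narrower. Most of the other tables are in-clinic measures at Baseline, and the rest record that an event or a gap occurred without saying whether the assigned dose could be sustained.

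A second reply concerns size. A reader might take it from the oral trials in protocol 1.2.2, where "48% of patients were dose-reduced or intermittently stopped due to AEs" and 14.8% discontinued (14.8/48 = 0.31). That ratio should not be used. The 48% is given without naming an arm, while 14.8% belongs to the 2403 mg/d arm. The 48% also includes interruptions, which both arms here may have, and it concerns oral dosing with far higher systemic exposure.

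A third reply is that a composite containing dose reduction is not neutral. Patients on 50 mg once daily cannot have that event in Part A, and in an open-label study a reduction may be made for milder intolerance than would lead to stopping. This also stands and shapes the remedy: the composite can support, but should not replace, the discontinuation row.

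**Conclusion.** The point holds as a reporting gap confined to Part A. Once patients are converted to 100 mg twice daily in Part B, the same reduction text applies to them. Within Part A, the discontinuation rows can understate treatment-limiting intolerance of 100 mg twice daily relative to 50 mg once daily. How far depends entirely on f: at f = 0 there is no effect, at 50% an assumed 10-point excess disappears, and at 75% it reverses. No planned hypothesis test of safety is affected.

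Two further inferences are tempting and go beyond the documents. One is that these tables favoured the regimen taken forward. The protocol attributes that choice to a DSMB review on 12 October 2020 that saw a trend in FVC, nine months before SAP version 3.0 (15 July 2021), and cites no discontinuation table. The other is that a patient reduced to 50 mg once daily will be moved into the 50 mg column. The SAP does not say so, and its Part B groups are built on the randomized arm. What the documents do show is an unreconciled difference between treatment received and randomized treatment, with nothing stating where such a patient is counted.

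**What to change.** - **SAP 10.1.** In the overall summary and in the tables by system organ class and preferred term, for Part A by randomized regimen, show separate rows for adverse events leading to dose reduction, to interruption and to discontinuation. Add a supportive row for any of the three beside the discontinuation row, with a footnote that reduction is not an available event for 50 mg once daily in Part A.
- **SAP 7.5.** Add, by arm, the number of patients with a dose reduction and the time to first reduction. Reconcile the ampoule count with protocol 8.8.1.
- **SAP 5.1.** Reconcile treatment received with protocol 11.2, so that a protocol-permitted reduction does not move a patient between columns in the Part A safety tables.

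The cost is a few table rows and one sentence. Protocol 10.1.4.3.1 already requires the action taken to be recorded for each adverse event, and SAP 7.5 already relies on recorded instructions to reduce or interrupt. This assumes the case report form distinguishes reduction from interruption, which the documents do not show. The downside is that the rows must be read together, since one of them can be filled by only one arm. No change to dosing or to the reduction rules is proposed.
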